## 9.6 Data management

#### 9.6.1 Data collection

The data required by the protocol will be collected in an eCRF and entered into a validated data management system that is compliant with all regulatory requirements. The web-based EDC system (provided by a vendor; Section 14) will aim to serve as an integrated, transparent tool to collect and manage data, and track study progress at the center and patient levels. Data collected specifically for the study will be kept in a central location. Data collected for the UNIFAI study will be held separately in the UNIFAI system.

Each investigator will have the ultimate responsibility for the collection and reporting of all data to the MAH's safety vendor or the eCRFs and any other data collection forms (source documents), while also ensuring that they are accurate, authentic/original, attributable, complete, consistent, legible, timely (contemporaneous), enduring, and available when required. The eCRFs must be electronically signed prior to database lock by the investigator to attest that the data contained in the eCRFs are correctly recorded. The MAH's designated representative will inform sites when it is time for eCRF sign-off to occur.

In the present case, the source documents are the patient medical charts and UNIFAI research records. Therefore, data collected in the eCRFs should match the data in the charts.

To ensure completeness and quality of the study-specific forms including safety data, reportable AE dates and results will be required fields in the EDC platforms, with manual queries utilized to obtain any missing components. Both the study-specific and separate UNIFAI EDC platforms have built-in edit checks, skip-logic, and manual queries for data coherence. The data management plan (Data Validation Manual) will include details documenting all aspects of queries, listings to identify data issues, resolutions for findings, and timings for queries and responses.

A data management plan (Data Validation Manual) will be prepared that details the data management and data handling procedures. This will include information on the data transfer procedures for analysis purposes.

## 9.6.2 Data monitoring

was chosen as the EDC platform, in part, to avoid duplicative training as site staff are already trained in the use of systems. Specific guidance on the data collection in this study are covered in the eCRF Completion Guidelines.

Final protocol version date: 16 December 2024

The CRO or designee (Section 14) will supervise and perform remote site management and monitoring, as described in the study-specific data management plan (Data Validation Manual) and the site monitoring plan. All participating sites will only have access to view and enter the data for their own patients. Only data required by the protocol for the purposes of the study should be collected.

All data entries in the study-specific EDC will be reviewed for clarity, uniqueness (non-duplication), completeness, and coherence in accordance with the data management plan (Data Validation Manual), edit checks, and manual queries. Missing, inconsistent, or unclear data will be queried as necessary throughout the study. Sites will be responsible for responding to queries in a reasonable timeline. The CRO or designee will also be responsible for the quality control of the study-specific database and confirming the overall integrity of the study-specific data. Quality-control mechanisms (eg, verification of data completeness, validations, skip-logic, and edit checks) are built into the EDC and employed at the time of data entry. Queries will be generated for resolution by site staff within the EDC system. The EDC system has built-in methods for data validation (eg, drop-down lists, value range controls, and standardized response formats) to minimize data entry errors; however, a data cleaning method will be employed to correct inconsistencies or errors that were not captured during data entry (eg, outliers or inconsistent data). Data queries will be identified on an ongoing basis during data collection. Sites will receive a regular e-mail notifying them of any new or outstanding queries. Formal source data verification is not expected in this study.

## 9.6.3 Record keeping

Investigators must keep relevant study documents, including site agreements, the identity of all participating patients (sufficient information to link records, eg, eCRFs and medical charts), source documents, detailed records of patient disposition (eg, signed informed consent), and adequate documentation of relevant correspondence (eg, letters, meeting minutes, telephone call reports). This will enable evaluations and/or audits from regulatory authorities or the MAH in accordance with national requirements on archiving of medical records. The records should be retained by the investigator for the length of time specified in local regulations, or in the Site Contract Agreement (whichever time period is longer).

If the investigator becomes unable for any reason (eg, retirement or relocation) to continue to retain study records for the required period, the MAH should be prospectively notified. The study records must be transferred to a designee acceptable to the MAH, such as another investigator, another institution, or to an independent third party arranged by the MAH. The investigator must obtain the MAH's written permission before disposing of any records, even if retention requirements have been met.

## 9.7 Data analysis

Details of the planned analyses are summarized below and will be described in a separate statistical analysis plan (SAP).

As previously described, post-baseline study data (including the reporting of any SAEs and potential DILI/CHF events) will only be collected prospectively (i.e. from enrollment into the study). Any retrospective data, changes in treatment regimen, or events that may have occurred between

Final protocol version date: 16 December 2024

omaveloxolone initiation and enrollment in patients in the non-naive cohort will not be collected and will therefore not form part of any analysis.

Data analyses will be presented separately for patients in the omaveloxolone-naive cohort and the non-naive cohort.

## 9.7.1 Statistical analysis plan

The SAP will describe analyses that will be performed for annual reports, as well as details of changes in the planned analysis after protocol finalization, if applicable. It will also provide a detailed description of the analyses to be performed and describe methods to address missing data.

All analyses will be conducted in accordance with the study objectives, SAP, and applicable guidelines.

## 9.7.2 Analysis populations

The study population will consist of patients with FA who receive omaveloxolone, according to prescribing information, and who are enrolled in the UNIFAI study. Patients who meet all inclusion criteria and none of the exclusion criteria are eligible to participate in the study and will constitute the main analysis population (also referred to as the safety analysis set).

## 9.7.3 Descriptive statistics

Descriptive statistics will be used to summarize the study data in tables, listings, and figures as appropriate at baseline and post-index timepoints. These will cover descriptive analyses of patient demographics, clinical history, disease characteristics, clinical management, . The BDI-2 will be scored as per the developer's guidelines. Continuous variables will be described with summary statistics such as n, mean, standard deviation, median, first quartile, third quartile, and minimum and maximum values. For each categorical variable, the frequency and percentage in each category will be reported. Percentages will be calculated using the specified denominator in the table. The frequency and percentage of patients with missing data for each data point will be presented. Two-sided CIs of 95% will be calculated when relevant. Exact 95% CIs will be calculated assuming a Poisson distribution. Percentages will be reported with one decimal place.

## 9.7.4 Primary analyses

#### All SAEs

An overall summary of TESAEs will be presented, consisting of the number and percentage of patients experiencing the total number of TESAEs. TESAEs will also be summarized by SOC and Preferred Term (PT) (see also Section 9.7.7). TESAEs will be presented overall and by severity and relationship to the omaveloxolone treatment.

Summary listings of TESAEs and SAEs by SOC and PT will be presented with all safety variables.

Where relevant, incidence rate variables will be described as event rates per patient-year (PY) while on treatment. Related two-sided 95% CIs will also be provided.

Final protocol version date: 16 December 2024

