#### Data analysis:

The analyses will be descriptive and presented separately for the omaveloxolone-naive cohort and non-naive cohort. Continuous variables will be described with summary statistics such as n, mean, standard deviation, median, first quartile, third quartile, and minimum and maximum values. For each categorical variable, the frequency and percentage will be reported.

Incidence rates will be calculated by dividing the number of new cases of SAEs (all) and all DILI and CHF AEs by the number of patient-years (PYs) at risk, which will be calculated over the follow-up period. In addition, 2-sided 95% confidence intervals (CIs) of incidence rates will be calculated.

There will be no imputation of missing data except for incomplete start dates for the purpose of time-to-event analyses.

A full annual report will be provided for EMA, and interim analyses on AEs of DILI and CHF are to be performed for the FDA biannually.

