  baseline data collection, certain laboratory assessments may be repeated if recommended by the
  treating physician and the results will be used as baseline for those variables. Patients will be
  allowed a maximum window of up to 6 months between enrollment and treatment initiation,
  beyond which they will be subject to re-evaluation for enrollment.
- For the non-naive cohort, baseline data will be collected retrospectively from patient medical records, the UNIFAI study database, and study site patient records looking back to the period prior to initiation of omaveloxolone treatment. Post-baseline data (including the reporting of any SAEs and DILI/CHF AEs) will only be collected prospectively from non-naive cohort patients beginning at their enrollment date. Any potential events that may have occurred between omaveloxolone initiation and enrollment will not be collected. Non-naive cohort patients will participate in the next scheduled assessment of the study visit cadence following their informed consent/assent.

Each patient's participation will last no longer than 60 months after omaveloxolone initiation although treatment is expected to continue past this timepoint. The follow-up period of 60 months after omaveloxolone initiation may end before 5 years in the following circumstances: if the patient dies, if the patient is lost to follow-up, or if the patient withdraws consent, or if the patient discontinues

Final protocol version date: 16 December 2024

omaveloxolone treatment. The end of follow-up in deceased patients will be defined as the date of death. The end of follow-up in patients lost to follow-up or who withdraw consent will be defined as the date of the last known assessment. If a patient permanently discontinues omaveloxolone treatment or discontinues from the study during the follow-up phase, the last follow-up visit will be 60 days after the last administration of omaveloxolone (unless discontinued due to death or withdrawal of consent).

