#### Long-term safety

The study will collect all SAEs regardless of causality assessment, and these will be coded using Medical Dictionary for Regulatory Activities (MedDRA) terminology. Incidence will be presented for all SAEs that occurred from the initiation date of omaveloxolone treatment for the omaveloxolone-naive cohort (with onset date on or after the first treatment of omaveloxolone) or from enrollment date for the non-naive cohort until study completion. In both cohorts, these are referred to as treatment-emergent SAEs

Final protocol version date: 16 December 2024

(TESEAs). The primary outcomes will be assessed via the safety event data collection that takes place during the omaveloxolone treatment period and up to 60 days following omaveloxolone discontinuation; this includes TESAEs that started or worsened after the first treatment.

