Descriptions of and incidence data for DILI and CHF events will be collected via the AE/SAE data collection forms. Incidence will be presented for all events of DILI and CHF that occurred from the initiation date of omaveloxolone treatment for the omaveloxolone-naive cohort (with onset date on or after the first treatment of omaveloxolone) or from enrollment date for the non-naive cohort until study completion.

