#### DILI and CHF AEs

Incidence rates of all DILI and CHF AEs will be estimated, with two-sided 95% CIs. The diagnostic variables (eg, liver panel, echocardiogram, and/or CHF panel) at the time of each DILI or CHF diagnosis will be summarized descriptively.

SAEs, DILI, and CHF outcomes may also be treated as time-to-event endpoints and analyzed using survival analysis approaches. More details are provided in the SAP.

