## 11.2.2 Recording of all DILI and CHF AEs and of all SAEs

Investigators should provide complete and accurate data on all events experienced for the duration of the recording period which are to be recorded on eCRFs on an ongoing basis for all DILI and CHF events and, for all SAEs, also via the additional reporting requirements described in Section 11.2.3.

Each report is to include a description of the event, whether it is considered serious (and if so, the criterion satisfied), its duration (onset and resolution dates), its relationship to omaveloxolone, any other potential causal factors, any treatment given or other action taken (including dose modification or discontinuation of omaveloxolone), and its outcome.

Investigators should use correct medical terminology/concepts when recording DILI and CHF AEs and all SAEs. Colloquialisms and abbreviations should be avoided. Only one AE term should be recorded per event.

Final protocol version date: 16 December 2024

All DILI and CHF AEs and all SAEs subject to the collecting and reporting requirements outlined in this protocol, whether reported by the patient or the treating physician, will be recorded in the patient's medical record and in the AE section of the eCRF.

Once an omaveloxolone-naive cohort patient signs informed consent in the study, all DILI and CHF AEs and all SAEs will be collected from the first omaveloxolone dose through 60 days following discontinuation of omaveloxolone. Once a non-naive cohort patient signs informed consent in the study, all DILI and CHF AEs and all SAEs will be collected from the date of enrollment through 60 days following discontinuation of omaveloxolone.

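### The primary incidence rates have two conflicting denominators, and the on-treatment one in Section 9.7.4 does not match the event window

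*Protocol*

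**What the plan says.** **Denominators.** The Data analysis part of the abstract (Section 4) covers SAEs and DILI and CHF events together and divides new cases "by the number of patient-years (PYs) at risk, which will be calculated over the follow-up period". Section 9.7.4, under All SAEs, says that, where relevant, "incidence rate variables will be described as event rates per patient-year (PY) while on treatment". The next paragraph of Section 9.7.4 says "Incidence rates of all DILI and CHF AEs will be estimated, with two-sided 95% CIs" and names no denominator.

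**Event window.** Section 9.3.1.1 assesses the primary outcomes "during the omaveloxolone treatment period and up to 60 days following omaveloxolone discontinuation". For DILI and CHF it counts events from first dose in the naive cohort, "or from enrollment date for the non-naive cohort until study completion". Section 11.2.2 agrees for the non-naive cohort: "CHF AEs and all SAEs will be collected from the date of enrollment through 60 days following discontinuation of omaveloxolone". Under Section 9.3.2.1 a patient who restarts within 60 days has had an interruption, not a discontinuation, so stays under observation while off drug.

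**Start of the clock.** Section 9.1.2 sets the index date at first dose (naive) or enrollment (non-naive). Section 9.7 keeps what happened between initiation and enrollment out of every analysis. Section 9.1.2 also contains this sentence: "The follow-up period of 60 months after omaveloxolone initiation may end before 5 years in the following circumstances".

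**The concern.** An incidence rate is interpretable only if every event in the numerator could have arisen in the person-time of the denominator. The protocol prescribes two denominators for the same primary result, and they cover different days. A SAP cannot follow both, and two analysts each following one passage would report different SAE rates.

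The on-treatment version also breaks the matching rule. An SAE 40 days after the last dose, or during a 30-day interruption, is counted, but the days on which it could occur are not. The rate is then too high. The error sits in patients who stop or pause the drug, who may not have the same event risk as the rest.

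The second issue is what the follow-up period means for non-naive patients. If it were taken to begin at initiation, the denominator would include up to 12 months in which no event is recorded, and the rate would be too low. The two errors run in opposite directions. These rates are the study's primary outcome and feed its repeated regulatory reports, so the definition should be settled before the first one.

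**Working it through.** **1. The plan's own figures.** Table 9-4, N = 300 over 5 years: 1,500 PY and x = (5/51) × 1,500 = 147.059 events. The exact Poisson limits are lower = χ²(0.025; 2x)/(2·PY) and upper = χ²(0.975; 2(x+1))/(2·PY). They give 0.083 to 0.115, as printed. All 9 rows of Table 9-4 and all 27 rows of Table 9-5 reproduce to three decimals. No stated figure is wrong. Both tables use PY = N × years, so they do not show which denominator is meant.

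**2. Numerator against denominator.**

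| Place | Days on which events count | Days in the denominator | Match? |
|---|---|---|---|
| Section 9.7.4, All SAEs | Index date to 60 days after discontinuation, interruptions included | On-drug days | No |
| Abstract, follow-up started at the index date | Same | Same | Yes |
| Abstract, follow-up started at initiation | Same | Adds pre-enrollment time (non-naive) | No |
| Section 9.7.4, DILI and CHF | Same | Not named | Open |

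The counts differ too: the abstract speaks of new cases, Section 9.7.4 of event rates.

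**3. Size of the 60-day tail over the study.** Table 9-6 expects 260, 230 and 180 patients to complete 1, 3 and 5 years. With linear interpolation from 300 at entry:

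- PY = 1 × (300 + 260)/2 + 2 × (260 + 230)/2 + 2 × (230 + 180)/2 = 280 + 490 + 410 = 1,180.
- Losses = 300 − 180 = 120. If all are discontinuations with a full tail: 120 × 60/365.25 = 19.7 PY.
- Overstatement = 19.7/1,180 = 1.7%. For year 1 alone: 40 × 60/365.25 = 6.6 PY, and 6.6/280 = 2.3%.

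This assumes the same event rate in the tail as on drug. If the tail rate were k times as high, the overstatement would be k × 1.7%. The protocol gives no frequency for interruptions, so they are not included.

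**4. Early cuts.** The protocol gives no early discontinuation share, so this is an assumption. Suppose a share d of patients stops, evenly spread over T years, and everyone is observed for T. On-drug time per patient is (1 − d)T + dT/2. The omitted tail is d times the mean of the smaller of 60 days and the time left to T.

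| d | T = 6 months | T = 12 months |
|---|---|---|
| 10% | 2.9% | 1.6% |
| 20% | 6.1% | 3.4% |
| 40% | 13.7% | 7.5% |

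**5. Non-naive cohort, only if person-time began at initiation.** Reported rate ÷ true rate = observed/(observed + unobserved). Unobserved time is an assumption; eligibility caps it below 12 months, taken here as 11.9.

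| Unobserved | 6 months observed | 1 year observed | Month 60 after initiation |
|---|---|---|---|
| 3 months | 67% | 80% | 95% |
| 6 months | 50% | 67% | 90% |
| 11.9 months | 34% | 50% | 80% |

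With 6 months unobserved and 6 observed, a true 0.098 per PY would be reported as 0.098 × 0.5 = 0.049. If person-time begins at enrollment, this error is zero.

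**The case against.** The strongest reply is that this is a wording inconsistency with little demonstrated effect. Several parts of it stand.

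- **The abstract's denominator can be right.** Section 9.1.2 starts following the patient after consent and puts the non-naive index date at enrollment. Section 9.3.1.1 presents non-naive incidence from enrollment, and Section 9.7 bars earlier data. Read with the words on being at risk, follow-up person-time fits the event window.
- **The mismatch in the text is small.** At most about 1.7% compares with a planned interval of 0.083 to 0.115 around 0.098, roughly ±16% (0.016/0.098). Deaths and consent withdrawals have no 60-day tail, so the true figure would be lower at a constant event rate.
- **The on-treatment wording has limited reach.** It stands under All SAEs and is qualified. Carrying it to DILI and CHF, the subject of the biannual FDA reports, is inference.

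A reader might go further and infer that neither denominator matches, and that the rates are therefore biased, most of all towards false reassurance in the non-naive cohort and the early reports. The documents do not support that. It requires counting pre-enrollment time, which no passage prescribes and several point against. The sentence about 60 months after initiation reads most naturally as a cap on participation. Section 9.3.4 derives a treatment duration but does not link it to any rate.

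The argument that person-time rules belong in the SAP does not dispose of the point. Silence could be left to the SAP. Two conflicting instructions for a primary analysis cannot, and neither can a denominator that disagrees with the protocol's own event window.

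**Conclusion.** The point holds in limited form. The abstract and Section 9.7.4 give different denominators for the primary SAE rate, and Section 9.7.4 leaves the DILI and CHF denominator unnamed. Followed as written, the on-treatment version counts off-drug events without person-time and slightly overstates the SAE rate. For the 60-day tail the ceiling is about 1.7% over the study, given linear attrition between the points of Table 9-6, every loss a discontinuation with a full tail, and a constant event rate. Early cuts could show more, about 3% to 14% at 6 months if 10% to 40% of patients stop; those shares are assumed.

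The follow-up denominator is sound if it starts at the index date, which is the better reading. Understatement in the non-naive cohort (about 10% at 60 months and 50% after 6 months observed, with an assumed mean of 6 months unobserved) is a risk from one loosely worded sentence in Section 9.1.2. It is not a consequence of the plan. The case for a change rests on the contradiction in a primary analysis and the ease of removing it, more than on the size of the demonstrated error.

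**What to change.** Put one definition in the abstract's Data analysis part and in both the All SAEs and the DILI and CHF paragraphs of Section 9.7.4:

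- **Person-time** starts at the index date (first dose for naive patients, enrollment for non-naive patients). It ends at the earliest of 60 days after the last dose, month 60 after initiation, death, or the last known assessment. Interruptions are included.
- **Numerator:** events that start or worsen within that same interval.
- **Type of rate:** say whether it counts first events, in which case a patient's person-time stops at the event, or all events.
- **On-treatment rate, if also wanted:** restrict both events and person-time to on-drug days after the index date, and label it separately.

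The cost is a few sentences in the protocol, mirrored in the SAP. The dates needed are already collected, so no new data are required.
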